13.3.2 Analysis of demographic and other baseline characteristics

Perform the following analysis in the "all enrolled subjects set" and "full analysis set".

In the analysis of the main subject demographic factors, frequency will be tabulated for discrete data, and summary statistics will be calculated for continuous data.

13.3.3 Efficacy analysis

13.3.3.1 Primary endpoint and analysis method

[Primary endpoint]

PFS rate 6 months after enrollment

The PFS rate 6 months after enrollment, the primary endpoint, is the gross proportion of surviving subjects without documented progression up to 6 months after enrollment, counting from the day of

CONFIDENTIAL

enrollment. Subjects with no imaging data on progression at 6 months after enrollment and subjects lost to follow-up will be included in the denominator, but will not be handled as progression-free.

The criteria for determining progression are described in “13.3.3.2 Secondary Endpoints and Analytical Methods for Them”.

[Main analysis]

The following analysis will be performed in the “full analysis set”.

PFS rate at 6 months is calculated by counting of subjects each subjects with progression, not progression, or unconfirmed at 6 months. “At 6 months” in the main analysis is defined as 24 weeks (8 weeks x 3) with time window of 2 weeks before and after. Based on the observed PFS rate at 6 months from the day of enrollment, binomial test will be conducted on the null hypothesis “value will be determined invalid at PFS rate $\leq 29\%$ ”. Significant level will be 2.5% (one-sided) in main analysis. For interval estimation, accurate 90% confidence interval (two-sided) based on binomial distribution will be used.

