6.2.2.2 Rationale for planned number of subjects

In the phase I part for the assessment of tolerability and RD of panitumumab and TAS-102 combination therapy, 6 to 12 subjects were included according to the “Guidelines for clinical evaluation methods of anti-cancer drugs” (PFSB/ELD notification No. 1101001, 01/Nov/2005).

Also, in this study as efficacy will be assessed on PFS rate as primary endpoint, according to the above guideline and precedent overseas clinical trial results, number of subjects were set as to confirm the expected PFS rate to overwhelm the PFS rate threshold.

In the panitumumab monotherapy vs. BSC as third-line treatment control trial in patients with unresectable, advanced/recurrent colorectal cancer (20020408 study⁴⁾), the PFS median were 8.0 weeks for the panitumumab group and 7.3 weeks for the BSC group. In retrospectively conducted *KRAS* wild-type population and *KRAS/NRAS* wild-type population, PFS median were 12.3 weeks and 14.1 weeks respectively in the panitumumab group. On the other hand, in the panitumumab monotherapy vs. cetuximab monotherapy control study (ASPECCT study) in patients with *KRAS* wild-type unresectable, advanced/recurrent colorectal cancer that became resistant to fluoropyrimidine agents, OXA, and IRI¹⁷⁾, the secondary endpoint PFS were 4.1 months for panitumumab and 4.4 months for cetuximab and showed no difference (hazard ratio [HR], 1.00; two-sided 95% confidence interval [CI], 0.88–1.14). Further, PFS rate at 6 months was 33% (two-sided 95% CI, 29% to 37%) for the panitumumab group.

[figure not shown]

Figure 6.b ASPECCT study Progression-free survival

On the other hand, for TAS-102, in the domestic phase II study in previously treated subjects with metastatic, unresectable, colorectal cancer refractory or intolerant to fluoropyrimidine agents, OXA, and IRI, and has treatment history of 2 regimens of standard chemotherapy, the secondary endpoint PFS median assessed by the Investigator were 1.0 months in the placebo group but significantly prolonged to 2.7 months in the TAS-102 group (HR = 0.35, two-sided 95% CI 0.25–0.50, $p<0.0001$)

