As increased anti-tumor effect can be expected by using TAS-102 in combination with panitumumab treatment which is the standard treatment for patients with unresectable, advanced/recurrent colorectal cancer, the PFS rate at 6 months in this study was assumed to be 48% and this was set as the expected value for the panitumumab treatment in combination with TAS-102 therapy in patients with RAS wild-type unresectable, advanced/recurrent colorectal cancer. *Also, for the threshold where* further development for panitumumab treatment in combination with TAS-102 may be considered not necessary, it was assumed to be 29% from the CI lower limit of the PFS rate at 6 months in the ASPECCT study.¹⁷⁾

For the main analysis, based on the observed PFS rate at 6 months from start of treatment, binomial test will be conducted on the null hypothesis “the true PFS rate at 6 months from start of treatment will be not more than the PFS threshold rate where value is determined invalid”. With the PFS threshold rate at 29%, PFS expected rate at 48% at 6 months from start of treatment, and one-sided significant level at 5%, power at 80%, the necessary number of subjects will be 47. Taking into consideration of ineligible or discontinued subjects at approximately 10%, the target number of subjects was set to 52 (including subjects that received RD in the phase I part).

6.3 Discontinuation of entire clinical study or discontinuation of clinical study at a study site

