7.2.4 Efficacy analysis

7.2.4.1 Primary endpoint and analysis method

[Primary endpoint]

Progression-free survival (PFS rate) at 6 months after enrollment

The PFS rate 6 months after enrollment, the primary endpoint, is the gross proportion of surviving subjects without documented progression up to 6 months after enrollment (date of enrollment + 24 weeks \pm 2 weeks), counting from the day of enrollment. Subjects with no imaging data on progression at 6 months after enrollment and subjects lost to follow-up will be included in the denominator, but will not be handled as progression-free.

Definition of progression:

Progression will include both progressive disease (PD) based on diagnostic imaging assessed according to RECIST ver. 1.1 and primary disease progression that cannot be confirmed by diagnostic imaging (clinical progression). When progression is documented by diagnostic imaging, the day on which the diagnostic imaging is performed will be the progression date. For clinical progression, the day of the clinical determination will be the progression date. In a case in which, for example, tumor diameter has become extremely small, if the status is determined to be “not definite progression” clinically, although the assessment is PD according to the response criteria, the assessment of PD according to the response criteria will take precedence and the status will be considered progression. (In this case, the clinical determination on continuing protocol treatment will take precedence.) Even if the assessment is not PD according to the response criteria, if there is

definite clinically documented progression, the clinical determination will take precedence and the status will be considered progression. For surviving subjects without documented progression, the period will be cut off on the final day when a progression-free status is confirmed (final day of progression-free survival confirmation). Confirmation of progression-free status by imaging test or sample test is not mandatory, and clinical confirmation by outpatient medical examination, etc., will be allowed. Contact by telephone only will not be allowed. Events and the cut-off will also be handled the same way in subjects who have discontinued protocol treatment for reasons such as toxicity and refusal of treatment, even if another (follow-up) therapy is added. Thus, the time of treatment discontinuation or the day of follow-up treatment initiation will not be the cut-off.

[Main analysis]

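### The primary endpoint is scored at 24 weeks ± 2 weeks but tested against a threshold taken from a 6-month PFS rate, and the plan does not align the two time points

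*Protocol*

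**What the plan says.** Protocol section 13.3.3.1 sets the scoring time: 6 months "in the main analysis is defined as 24 weeks (8 weeks x 3) with time window of 2 weeks before and after". SAP version 4.0, section 7.2.4.1, says the same. The endpoint "is the gross proportion of surviving subjects without documented progression up to 6 months after enrollment", with the time point given as "date of enrollment + 24 weeks" plus or minus 2 weeks.

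Protocol section 6.2.2.2 gives the source of the threshold. For the reference trial, "PFS rate at 6 months was 33% (two-sided 95% CI, 29% to 37%) for the panitumumab group", and for the value at which development would stop, "it was assumed to be 29% from the CI lower limit of the PFS rate at 6 months in the ASPECCT study". The expected rate is on the same footing: "the PFS rate at 6 months in this study was assumed to be 48"%.

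Neither document converts the reference rate from 6 months to 24 weeks, or says how many days the reference trial's 6 months was. Neither says which assessment decides the status when a subject has one early in the window and an event later in it.

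The significance level is stated in two ways. It is one-sided 5% in the protocol summary (2.0), 6.2.2.2 and 13.3.3.4, and in SAP 7.2.4.5. It is one-sided 2.5% in protocol 13.3.3.1 and SAP 7.2.4.1.

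**The concern.** A PFS curve cannot rise, so a rate read before month 6 is at least as high as the rate at month 6. The reference curve was falling quickly in this region: "the secondary endpoint PFS were 4.1 months for panitumumab and 4.4 months for cetuximab and showed no difference", and only 33% remained progression-free at 6 months. A subject called progression-free on day 154 or day 168 has had less time to progress than subjects in the benchmark had. At stake is the single primary test, which turns on one or two subjects out of 52.

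**Working it through.** **Inputs.** Threshold 29%, expected rate 48%, one-sided 5%, power 80%, N = 47 and target 52 (protocol 6.2.2.2). Reference median 4.1 months and 33% at 6 months (same section). Scoring at day 168, window day 154 to 182 (13.3.3.1). Imaging every 56 days from Course 1 Day 1 (9.2.10). Treatment start in principle within 14 days of entry (8.1).

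**Assumptions not in the documents.** The reference trial used calendar months (6 months = 182.6 days), and PFS falls smoothly.

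**Step 1: reproduce the plan's figure.** The protocol states "one-sided significant level at 5%, power at 80%, the necessary number of subjects will be 47". With an exact binomial test, N = 47 and success at 20 or more, size is P(X ≥ 20 | 47, 0.29) = 0.033 and power is P(X ≥ 20 | 47, 0.48) = 0.814. From N = 47 upwards, power stays above 80%. The figure reproduces.

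**Step 2: the rule at N = 52, for the null as written.**
- One-sided 5%: success at 22 or more, size 0.028, power at 48% 0.831.
- One-sided 2.5%: success at 23 or more, size 0.014, power at 48% 0.752.

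The exact test is within its level in both cases.

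**Step 3: carry 29% at 6 months back to the scoring day.** With an exponential curve, p(d) = 0.29^(d/182.6). At day 168, p = 0.29^0.920 = 0.320. As a check, use the hazard implied by the reference figures: ln(0.50/0.33)/(6 − 4.1) = 0.2187 per month. Day 168 is 168/30.44 = 5.52 months, so p = 0.29 × exp(0.2187 × 0.48) = 0.322.

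**Step 4: chance of a positive result at those rates, N = 52 (exponential curve).**

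| Scoring day | Rate matching 29% at 6 months | 22 or more (nominal 5%) | 23 or more (nominal 2.5%) |
|---|---|---|---|
| 154 | 0.352 | 0.177 | 0.113 |
| 168 | 0.320 | 0.077 | 0.044 |
| 175 | 0.305 | 0.048 | 0.026 |
| 182 | 0.291 | 0.029 | 0.015 |

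With 0.322 at day 168 the two probabilities are 0.081 and 0.046. If the reference month was 28 days, 6 months is day 168 and the shift is zero.

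**Step 5: where scans fall.** The third scan is due 168 days after treatment start. With a lag of 0 to 14 days, that is day 168 to 182 from enrollment. With the ± 7 day allowance in Table 9.c it is day 161 to 189, so an on-schedule third scan does not fall on days 154 to 160.

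**Step 6: the offset from unconfirmed subjects.** Subjects with no imaging data at 6 months, or lost to follow-up, count as not progression-free. The share of truly progression-free subjects who would have to be unconfirmed to cancel the shift is 1 − 0.29/0.320 = 9.4%, or 1 − 0.29/0.322 = 9.9%.

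**The case against.** The strongest objection is that the plan tests a stated null, a rate of at most 29% under its own scoring rule, and the exact test holds its level for that null. This stands. A reader might infer that the type I error exceeds 5%. The documents do not support that as a plain statement: the excess exists only against a benchmark moved to the scoring day.

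The size of the move is also uncertain, mostly in the direction of smaller:
- Imaging runs from treatment start. With a 7-day lag (assumed), the third scan is due on day 175; the matched rate is 30.5% and the chance of a positive result is about 5% at the 5% rule.
- Radiological progression is dated to the scan. Between week 24 and month 6 no further scan is scheduled, so only clinical progression, deaths and late scans add events. If the reference trial also scanned at week 24 (its schedule is not given), both rates rest largely on that scan and the smooth curve overstates the gap.
- Counting unconfirmed subjects as failures pulls the other way, and about 10% would cancel the shift. This is real, but it depends on missing data and is no substitute for a matched definition.
- If the window is read as counting every event up to its upper edge, day 182, the gap is about 0.1 point. The text does not say that this is the reading.

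A reader might also infer that the false positives described here are those of a regimen that adds nothing to panitumumab. That would be a regimen at the reference rate of 33%, which passes 10.2% of the time at 22 or more of 52 with no timing mismatch at all. That follows from setting the threshold at the lower confidence limit, which is a separate choice.

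**Conclusion.** The mismatch is in the text and is not justified there: a 24-week score, with a window opening at day 154, is compared with a 6-month benchmark. Its effect is modest and conditional. With calendar months in the reference trial, a smooth curve and scoring at day 168, the matched threshold is about 32% rather than 29%. The chance of a positive result at that rate is about 8% at nominal 5% and about 4.5% at nominal 2.5%. Over the window the matched rate runs from about 35% (day 154) to 29% (day 182), and with 28-day months there is no shift.

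The statement that the null is 3 points too low is therefore one point in a range and not a finding from the documents. The two significance levels matter about as much as the timing, since each moves the cut-off by one subject (22 or 23 of 52). They have to be reconciled whichever way the timing is settled.

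**What to change.** Keep the 29% threshold. In protocol 13.3.3.1 and SAP 7.2.4.1, state that any progression, radiological or clinical, or any death documented through day 182 from enrollment is a failure, even if an earlier scan in the window showed no progression. Report the Kaplan-Meier PFS estimate at 6 months (day 183) with its confidence interval beside the crude rate, as a sensitivity analysis. The SAP already plans Kaplan-Meier estimates at specified time points, so this only names one. State a single significance level for the main analysis throughout both documents.

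The cost is a few sentences and no new data. The observed rate may be slightly less favourable, because events between an early scan and day 182 now count.

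Do not replace 29% with the reference curve's value at 24 weeks. On the assumptions above that value is 0.33 × exp(0.2187 × 0.48) = 36.7%, the point estimate rather than the lower limit. At nominal 5% it would raise the cut-off to 26 of 52. Moving 48% to 24 weeks in the same way, 0.48^0.920 = 50.9%, power would then be about 61%. That is a different benchmark and would change the design.

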PFS rate at 6 months is the crude rate of subjects who survived or were not determined as progressive at 6 months from the day of enrollment. Based on the observed PFS rate at 6 months from the day of enrollment, binomial test will be conducted on the null hypothesis “value will be determined invalid at PFS rate $\leq 29\%$ ”. Significant level will be 5% (one-sided) in main analysis. For interval estimation, accurate 90% confidence interval (two-sided) based on binomial distribution will be used.

PFS is the period from the day of enrollment until the day of documented progression or the day of death due to all causes whichever comes earlier. Kaplan-Meier method will be used to illustrate progression free curve and quantile point and its 95% confidence interval (two-sided) of PFS will be calculated.

Rationale for planned number of subjects:

[figure not shown]
In the phase I part for the assessment of tolerability, 6 to 12 subjects were included according to the

CONFIDENTIAL

“Guidelines for clinical evaluation methods of anti-cancer drugs” (PFSB/ELD notification No. 1101001, 01/Nov/2005).

Also, in the phase II part as efficacy will be assessed on PFS rate at 6 months as primary endpoint, according to the above guideline and precedent overseas clinical trial results, number of subjects were set as to confirm the expected PFS rate to overwhelm the PFS rate threshold.

In the panitumumab monotherapy vs. best supportive care (BSC) as third-line treatment control trial in patients with unresectable, advanced/recurrent colorectal cancer (trial 20020408), the PFS median, the primary endpoint, were 8.0 weeks for the panitumumab group and 7.3 weeks for the BSC group. In retrospectively conducted *KRAS* wild-type population and *KRAS/NRAS* wild-type population, PFS median were 12.3 weeks and 14.1 weeks respectively in the panitumumab group. On the other hand, in the panitumumab monotherapy vs. cetuximab monotherapy control study (ASPECCT study) in patients with *KRAS* wild-type unresectable, advanced/recurrent colorectal cancer that became resistant to fluoropyrimidine agents, OXA, and IRI, the secondary endpoint PFS were 4.1 months for panitumumab and 4.4 months for cetuximab and showed no difference (hazard ratio [HR], 1.00; two-sided 95% confidence interval [CI], 0.88–1.14). Further, PFS rate at 6 months was 33% (two-sided 95% CI, 29% to 37%) for the panitumumab group.

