13.3.3.4 Level of significance, confidence coefficient

- Significance level: Main analysis only, 5% (one-sided); other analyses, 5% (two-sided)
- Confidence coefficient: Main analysis only, 90% (two-sided); other analyses, 95% (two-sided)

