
The following analysis will be performed on the “full analysis set.”

PFS rate at 6 months is calculated by counting of subjects with progression, without progression, and unconfirmed at 6 months. Based on the observed PFS rate at 6 months from the day of enrollment, binomial test will be conducted on the null hypothesis “value will be determined invalid at PFS rate $\leq 29\%$.” Significant level will be 2.5% (one-sided) in the main analysis. For interval estimation, accurate 90% confidence interval (two-sided) based on binomial distribution will be used.

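### The primary test has two significance levels: one-sided 2.5% in the main-analysis text and one-sided 5% in the sample-size and significance-level sections; at 2.5% the design falls short of its stated 80% power

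*Protocol*

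**What the plan says.** Two levels are given for the one primary hypothesis test.

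**One-sided 2.5%**
- Protocol 13.3.3.1, main analysis: "Significant level will be 2.5% (one-sided) in main analysis".
- SAP v4.0, 7.2.4.1, main analysis: "Significant level will be 2.5% (one-sided) in the main analysis".

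**One-sided 5%**
- Protocol 2.0, statistical method: "Significant level will be 5% (one-sided) in main analysis".
- Protocol 6.2.2.2: "one-sided significant level at 5%, power at 80%, the necessary number of subjects will be 47". The sample-size text in the study summary gives the same level.
- Protocol 13.3.3.4: "Significance level: Main analysis only, 5% (one-sided); other analyses, 5% (two-sided"). SAP v4.0, 7.2.4.5, says the same.

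The interval for the primary endpoint is a two-sided exact 90% interval in every one of these analysis sections, including the two that set the test at 2.5%.

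**The concern.** A one-sided 5% test and a two-sided 90% interval are two forms of one rule: the test rejects 29% when the lower limit lies above 29%. A one-sided 2.5% test pairs with a 95% interval. The main-analysis paragraphs of both documents join a 2.5% test to a 90% interval, so the test can fail while the reported interval excludes the threshold.

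Two things are at stake. First, the trial has a single primary test, and its success criterion differs by one subject depending on which section is followed. The study is open-label and single-arm, so the level could be settled after the count is known. Second, the sample size was justified at 5%, so a test run at 2.5% does not have the power the protocol claims.

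**Working it through.** **Inputs**
- Threshold p0 = 0.29 and expected rate p1 = 0.48 (Protocol 6.2.2.2: "With the PFS threshold rate at 29%, PFS expected rate at 48% at 6 months from start of treatment").
- Stated level 5% one-sided, power 80%, n = 47 (6.2.2.2).
- Target: "Taking into consideration of ineligible or discontinued subjects at approximately 10%, the target number of subjects was set to 52".
- Test (13.3.3.1): "binomial test will be conducted on the null hypothesis" of a rate no higher than 29%. It is taken as exact, in line with the exact binomial interval specified beside it.

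**Formulas**
- Critical count: c = the smallest c with P(X ≥ c | n, 0.29) ≤ α.
- Power = P(X ≥ c | n, 0.48).
- Intervals are Clopper-Pearson.

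**Reproducing the plan's 47.** At α = 5%, exact power first reaches 80% at n = 40 (80.3%), then moves up and down as the critical count steps. The last dip below 80% is at n = 46 (77.6%). From n = 47 (81.4%) it stays at or above 80%, so 47 reproduces under that rule. The allowance follows: 47 × 1.1 = 51.7, rounded up to 52. At α = 2.5% the same rule gives n = 56 (first reached at 54).

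**Both levels side by side**

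| Analysed n | Level | Successes needed | Actual α | Power at 48% |
|---|---|---|---|---|
| 47 | 5% | 20 (42.6%) | 3.3% | 81.4% |
| 47 | 2.5% | 21 (44.7%) | 1.6% | 72.6% |
| 52 | 5% | 22 (42.3%) | 2.8% | 83.2% |
| 52 | 2.5% | 23 (44.2%) | 1.4% | 75.2% |

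Power at 2.5% for n = 47 to 54 is 72.6, 76.8, 71.8, 76.0, 79.8, 75.2, 79.0 and 82.4%. It is below 80% at every n from 47 to 53.

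**Where the verdict changes, n = 52**

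| Count | Exact one-sided p | At 5% | At 2.5% |
|---|---|---|---|
| 21 | 0.0519 | fail | fail |
| 22 | 0.0278 | pass | fail |
| 23 | 0.0139 | pass | pass |

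For 22/52 the exact 90% interval is 30.7% to 54.6%, which excludes 29%. The exact 95% lower limit is 28.7%, which does not. If the true rate is 48%, exactly 22 occurs with probability 0.8315 − 0.7521 = 0.079.

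The disputed count moves with the size of the full analysis set: 20 for n = 47 or 48, 21 for n = 49 to 51, and 22 for n = 52.

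**The case against.** **The intended level can be inferred.** Most of the current text says 5%, including both sections devoted to the significance level, and the 90% interval agrees. The superseded protocol in the same file has 2.5% in its study summary, where the current one has 5%, so the 2.5% in 13.3.3.1 looks like an unfinished edit. That is a good reason to resolve the conflict at 5%. It does not remove the conflict, because no section is given precedence and the 2.5% stands in the paragraphs that define the main analysis.

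**n = 47 does not by itself identify the level.** The normal approximation with null and alternative variances gives 37.7 at 5% and 47.5 at 2.5%. The exact derivation also needs a rule that power stays above 80%, which the protocol does not state. This stands. The evidence for 5% is the level written in 6.2.2.2, the two significance-level sections and the 90% interval.

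**The figures assume an exact test.** With an uncorrected normal approximation, 22/52 gives z = 2.11 and p about 0.017, which passes at both levels, and power at 2.5% would be about 80% for n = 47 and 83% for n = 52. The disagreement then moves down one count: 21/52 gives p about 0.035. So the power loss depends on the exact test, but the ambiguous verdict does not.

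**The study is exploratory and type I error stays under 5% either way.** Both are true with the exact test. Neither tells the analyst whether a borderline count is a success.

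**Conclusion.** The concern holds. The current protocol and SAP v4.0 each give one-sided 2.5% and one-sided 5% for the same primary test, and neither says which prevails. The 90% interval and the stated sample-size basis fit 5%.

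If the main-analysis text is followed, exact power lies between 71.8% and 79.8% for 47 to 52 analysed subjects, against the stated 80%; the shortfall is 0.2 to 8.2 percentage points. If 5% is followed, power is at least 80% throughout that range. The verdict is in dispute at one count for each n, with a probability of roughly 7% to 9% if the true rate is 48%.

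These sizes rest on an exact binomial test and on the protocol's 29% and 48%. The contradiction itself rests on no assumption and needs correcting before the primary result is interpreted.

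**What to change.** - In Protocol 13.3.3.1 and SAP 7.2.4.1, change the one-sided level from 2.5% to 5%. They then agree with the study summary, 6.2.2.2, 13.3.3.4, SAP 7.2.4.5 and the 90% interval.
- State that the test is exact and that success means one-sided p ≤ 0.05 in the full analysis set. Give the critical count as at least 22 if 52 are analysed, and make clear that the p-value rule governs at any other size (20 for 47 or 48 analysed, 21 for 49 to 51).
- If 2.5% is really intended, correct the sections that say 5%, report a 95% interval, and restate power as about 75% with 52 analysed. Keeping 80% would need about 54 to 56 analysable subjects.

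The recommended change is one number in two sections plus a sentence on the decision rule. It needs no further patients, procedures or data.
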